[contact] – a mixed-method, stepped-wedge, randomized controlled trial to assess a clinical pathway for home-dwelling people with dementia and their caregivers

Statistical Analysis Plan (SAP)

Version 17.01.2023

NFR Project number 273581

Introduction

Preface

The objective of the Statistical Analysis Plan (SAP) is to outline the statistical methodology to be used for the final analysis of [[contact]](#)[1].

The SAP is based on the following documents

Study Protocol	Version 4.0 (26.04.2019)
Amendments to Study Protocol / Observational Plan	Change in protocol due to Covid-19 restrictions. Approval for change from Regional Ethical Committee (REK: 10861, 06.04.2020), update clinicaltrials.gov (31.08.2020)
Scientific Review Committee Charter (SRC)	22.11.2017 Research Council Norway granted the [contact] allocation 19.06.2018 Date for signing the contract 06.05.2019 Approval Ethic Committee (2019/385/REK North)
Professional development Plan (PD)	Post-doc 1: 20210311 Post-doc 2: 20211209 Post-doc 3: 20201209
Statistical Analysis Plan for the Interim Analyses	Not applicable

Timing of statistical analyses

Final analysis after the last data collection period is completed.

Modification History

Changes to the study protocol

Protocol version 4.0 was changed in April 2020 due to the Covid-19 restrictions, as the pandemic severely hampered the implementation of the intervention which had to be delivered at the participants homes. We therefore had to change the design of the overall trial, postponing the intervention in two municipalities and delivering the intervention by phone in the last municipality. In addition, we initiated the PAN.DEM cohort in the [contact] trial, collecting data from phone interviews with caregivers on change in health service use and neuropsychiatric symptoms, risk perception and restrictions [2]. Changes in design approved by Ethical committee (REK: 10861), update on clinicaltrials.gov (31.08.2020)

Study Design

Indication	
Design	Stepped-wedge design

	Closed cohort where individuals are identified at the start of the trial and scheduled for repeated outcome assessment [3]
Phase	

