Planned enrolment	3 municipalities and 9 municipality districts

Sample size estimation

The required sample size calculated before recruitment of participants aimed to detect a difference of 7 h/week for the primary outcome RUD. Based on the literature[4], we assumed that the number of hours of informal care is 46 h/week with a standard deviation (SD) of 20 h/week. With 80% power and a significance level of 5%, the required sample size was estimated to be 260 dyads. To allow for 20% loss to follow-up, a total of 315 dyads, equaling 105 per municipality, must be included.

The post-hoc sample size calculations based on the outcome PADL showed that by treating the study as an individually randomized stepped wedge design[3], with 3 intervention sequences, 5 periods, effect size of 7h/week, outcome variance of 400, significance level of 5% and within-individual correlation of 0.1075 over the 24 month trial would require a total of 240 dyads to be included. To allow for 20% loss to follow-up, the sample size must reach 288 dyads.

Randomization, blinding and unblinding procedures

Block randomization was performed using a computerized random number generator to allocate individual dyads to the three intervention sequences. We will apply stratification to secure that about one third of the dyads in each treatment sequence will be recruited from each municipality. Research assistants, researchers conducting the analyses and other study personal conducting data collection will be blinded to the randomization order, the dyads will be blinded to group allocation until contacted by their coordinator at start of the intervention period. Given the practice change of the intervention, the municipality home care services and coordinators will be informed about allocation sequence when their clusters entered the intervention period.

Analysis Sets

Full Analysis Set (FAS)

The intention-to-treat population includes all randomized dyads who were assigned a coordinator by the municipality. The dyads will be analyzed separately (i.e., PwD and caregiver), dependent on outcome of interest.

This will be the primary analysis set for baseline summary statistics of demographics, primary, secondary and exploratory efficacy analysis as elaborated in section 10.

Municipal coordinator set (MCS)

All coordinators in all municipality districts

Usage overview of analysis sets table

Analyses	FAS	MCS	
Disposition			
Demographics and background	x		
Medical history			

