Efficacy: primary	x		
Efficacy: secondary	x		x
Efficacy: other	x	x	x

General Statistical Methods and Definitions

General statistical methods

The statistical analysis will be presented by treatment group for the different analysis sets as outlined in section 4.

Stepped wedge design (SWD) do not strictly feature a treatment and control group, and thus, the summary statistics will include all participants at baseline, and the characteristics according to intervention sequences.

Continuous variables will be summarized using descriptive statistics (means and interquartile ranges), and categorical variables will be presented by frequencies and percentages. A table will present the number of caregivers and PwD with the following data: missing values, mean, median, standard deviation and confidence intervals.

Means and median as well as percentages will be presented with 1 additional decimal place and standard deviation by 2 additional decimals.

If the number of PwD or caregivers in a category is 0, then percentage will not be displayed.

P-values will be reported to 3 decimal places.

Unless otherwise specified, all statistical tests will be two-sided.

Causal model

Due to the longitudinal structure of the collected trial data, we considered the following linear mixed model to estimate and identify the treatment effect due to the intervention. Our SWD, consisting of $j = 3$ municipalities and 3 steps, is a closed cohort design, and thus, time related confounders are important to adjust for [5] when assessing treatment effect.

Mixed-effects regression is one of the most common approaches when estimating the intervention effect in SWD [6, 7]. In our design, we will consider the following model as our primary analysis model, assuming a constant treatment effect.

$$(1) Y_{ijt} = \beta_0 + O_{ijt}\beta_1 + X_{ijt}\beta_2 + b_i + \epsilon_{ijt}$$

where notation Y_{ijt} refers to the primary outcome caregiver burden (RUD and RSS), elaborated in section 3 Study Design, for individual i nested in municipality j at time point t . O_{ijt} is the treatment indicator (effect of receiving assistance from a municipality coordinator) and β_1 is the average treatment effect parameter of interest. Since the study collects repeated observations from the same participants, we consider a longitudinal regression model that adjusts for participant-level random effect, $b_i \sim N(0, \sigma_b^2)$, which corresponds to a compound symmetric correlation structure.

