In cost-effectiveness analysis the effect is measured in health units (or other outcome measures depending on the context). The outcomes are common health measures in natural units, and the results are presented as cost per effect unit/outcome measure. In cost-utility analysis, also called cost per QALY analysis, the effect is measured as quality-adjusted life years (QALYs) on a scale of 0 (death) and 1 (full health). A quality-adjusted life year (QALY) captures both life years gained and improved health as a result of treatment [8, 9].

The economic evaluation will be measured at society level.

Costs and QALYs will be measured for each phase of 6 months

The cost-effective analysis will relate the difference in total mean costs at societal level per 6 months between all intervention -and usual care phases to the difference in RUD, RSS, QoLs, QALYs, NPI, function level such as ADL and IADL

The analysis will use a discounting rate at 3.5%.

Following other costs studies calculating RUD in an advanced economy setting, our analysis will use 35% of the Norwegian average income to value lost leisure time for retired caregiver.

The primary economic evaluation will use the opportunity cost method to assess the costs of informal caregiving. For a sensitivity analysis, the replacement cost will be used.

Unit costs will be based on information from Statistics Norway and information from the primary health care institutions in each municipalities.

Covariates and strata

In the main statistical analyses, the following covariates are used for both caregivers and PwD.

For PwD: Age, sex, marital status, cohabitation status, number of co-caregivers, clinical characteristics of dementia (dementia etiology, neuropsychiatric symptoms, functional level)

For Caregivers: Age, sex, marital status, cohabitation status, numbers of co-caregivers involved in caregiving for the PwD, work status, use of health care services,

Groups, municipalities

Municipalities will be grouped in the main analysis and used as an adjustment variable (fixed effects). This is not the case for district municipalities as we consider that the dyads are similar within municipalities

Subgroups

In subgroup analyses, the following covariates will be used to define relevant subgroups:

- Gender (male, female)
- Work (retired and working caregivers)
- Caregiver relation (spouse, children)
- Residency (living alone, or with caregiver)

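### If the pandemic made exposure timing differ between municipalities, a municipality main effect lets part of any municipality-specific change into the treatment effect; municipality-by-period effects prevent this at little cost

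*SAP*

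**What the plan says.** **Allocation.** Randomization, blinding and unblinding procedures: individual dyads were randomised to three sequences, and "We will apply stratification to secure that about one third of the dyads in each treatment sequence will be recruited from each municipality". Sequence is therefore balanced within municipality by design.

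**Schedule.** The caption under Study periods and the delta table under Intervention effect each show one crossover schedule by group. Neither gives a separate schedule for any municipality.

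**What changed.** Modification History describes "postponing the intervention in two municipalities and delivering the intervention by phone in the last municipality". Exposure and Compliance, Treatment groups, confirms that the randomised sequence was departed from during the first lockdown. Neither place gives the length of the postponement, the groups affected, or whether the assessments moved too.

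**Model.** Model (1) under Causal model contains a treatment indicator defined by receiving coordinator assistance, covariates with the stratification variables, and a participant random intercept. No period term is written, although the same section calls time-related confounding important. On municipality, Covariates and strata says: "Municipalities will be grouped in the main analysis and used as an adjustment variable (fixed effects". No model or sensitivity analysis in the SAP has a municipality-by-time term.

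**The concern.** While all municipalities cross over together, the proportion of treated dyads in each period is the same in each of them. A municipality main effect is then sufficient, given common period terms.

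The pandemic change was made by municipality, which was not randomised. If it moved exposure by a whole assessment period in some municipalities, the same calendar period contains different treated proportions in different municipalities. A model with municipality and common period effects uses that contrast as information on treatment. If infection rates, closures or local services changed informal care differently across municipalities, part of that difference is credited to LIVE or charged against it. More hours in the postponed municipalities would look like a benefit of LIVE. More hours in the municipality that stayed on schedule would look like harm.

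The lockdown analysis does not cover this. It lets the treatment effect vary by group and period, carries no municipality index, and leaves the untreated background common to all municipalities.

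**Working it through.** **1. The plan's own figures.** The calculation "aimed to detect a difference of 7 h/week for the primary outcome RUD" and assumed "46 h/week with a standard deviation (SD) of 20 h/week". Two-sided 5%, 80% power: n per group = 2 × (1.96 + 0.842)² × 20² / 7² = 128.1, so 129 per group and 258 in total, against 260 stated. The post-hoc 240 (3 sequences, 5 periods, variance 400, correlation 0.1075) was checked with the model of step 2 under the planned schedule. SE = 1.942 h/week and 7/1.942 − 1.96 = 1.64, which is 95% power. The SAP states no power there. The set-up thus reproduces both figures.

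**2. Set-up.** From the SAP: 315 dyads, 105 per municipality, so 35 per municipality-by-sequence cell; assessments at months 0, 6, 12, 18 and 24; within-dyad covariance V = 400[(1 − ρ)I + ρJ]. Exposure is kept after the start. Common period terms are included, although model (1) does not show them, so that only the municipality issue is measured. If s is the municipality-specific shift, the bias in β1 is the treatment element of (X′V⁻¹X)⁻¹X′V⁻¹s.

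**3. Assumptions not in the SAP.** A one-period delay of group 2, or of groups 2 and 3, in two municipalities; the third stays on schedule; a shift of 5 h/week in that third municipality. Bias is proportional to the shift.

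**4. Where the leak arises.** Proportion of dyads treated:

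| Month | 0 | 6 | 12 | 18 | 24 |
|---|---|---|---|---|---|
| Common schedule | 0 | 1/3 | 2/3 | 1 | 1 |
| Group 2 delayed | 0 | 1/3 | 1/3 | 1 | 1 |
| Groups 2 and 3 delayed | 0 | 1/3 | 1/3 | 2/3 | 1 |

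If every municipality follows the first row, municipalities do not differ in any period and the leak is 0. If two follow the second row, they differ from the third by 1/3 at month 12. If two follow the third row, they differ by 1/3 at months 12 and 18.

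**5. Results at ρ = 0.1075, N = 315.**

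| Delay | Shift lasts | Bias (h/week) | Share of shift | Bias/SE |
|---|---|---|---|---|
| Group 2 | month 12 | 0.74 | 14.7% | 0.44 |
| Group 2 | months 12–18 | 0.55 | 11.0% | 0.33 |
| Group 2 | months 12–24 | 0.37 | 7.4% | 0.22 |
| Groups 2 and 3 | month 12 | 0.42 | 8.4% | 0.29 |
| Groups 2 and 3 | months 12–18 | 0.84 | 16.8% | 0.57 |
| Groups 2 and 3 | months 12–24 | 0.56 | 11.2% | 0.38 |

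SE is 1.677 (group 2) and 1.466 (groups 2 and 3). Against the 7 h/week target the bias is 0.37/7 = 5% to 0.84/7 = 12%. Rejection under the null is 5.6–8.9% instead of 5%.

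**6. Hand check.** The between-municipality contrast carries a share 1 − 1/R² of the information, where R is the SE with municipality-by-period effects divided by the SE without. Where the shift falls exactly on the periods that differ, that contrast is wrong by shift ÷ (1/3) = 3 × shift. Group 2, month 12: R = 1.0255, share 4.9%, × 3 = 14.7%. Groups 2 and 3, months 12–18: R = 1.0293, share 5.6%, × 3 = 16.8%. Both agree with the table.

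**7. Range.** At an assumed ρ of 0.7 the largest share is 23% (1.14 h/week, about 1.2 SE). If all three groups are delayed and a 7 h/week shift in the postponed municipalities lasts to month 24, the bias at ρ = 0.1075 is −0.24 h/week, and 0.24/7 is about 3%.

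**8. With municipality-by-period effects.** The bias is 0.00 in every scenario. The SE ratio is 1.000 under the planned schedule, 1.025–1.033 with group 2 delayed and 1.029–1.040 with groups 2 and 3 delayed (ρ from 0.1075 to 0.7). With all groups delayed it reaches 1.046 at ρ = 0.8.

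**The case against.** The strongest objection is that the SAP does not establish the premise. It says that the intervention was postponed in two municipalities, but not by how long or for which groups. A delay that stays inside a six-month period would leave the period coding unchanged. The schedules in this SAP, dated January 2023 and so written after the change, are common to all municipalities; coded that way, the leak is exactly 0. This stands. A reader might infer that the primary estimate is known to mix randomised and non-randomised comparisons. The documents make that plausible, through the receipt-based indicator and the acknowledged deviations, but do not settle it.

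A reader might also infer that any difference between municipalities passes in full into β1. It does not: in these scenarios at most about a quarter does. The figure of about 1.2 SE needs a correlation of 0.7, which is not in the SAP.

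The missing period term in model (1) matters more. Without it, a 5 h/week shift common to all municipalities from month 12 onward biases β1 by 3.0–3.8 h/week at ρ = 0.1075. This also stands, and the present point is a refinement beside it. The proposed terms would cure both.

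Finally, municipality fixed effects with a constant treatment effect are a recognisable primary model, and the SAP promises several robustness analyses. Those it lists are subgroup and item-level analyses and cost simulations, and none removes a municipality-specific background change.

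**Conclusion.** The point holds in conditional form. The SAP records a change of intervention timing by municipality, codes treatment by receipt, and adjusts for municipality only as a constant. If realised exposure by period differs between municipalities, β1 is partly a non-randomised contrast, and common period terms do not remove it.

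The size is moderate: 7–17% of a municipality-specific shift at the stated correlation, under the assumed one-period delays of group 2 or of groups 2 and 3. The direction depends on which municipalities were hit harder. These figures rest on a linear model with complete data and on a delay pattern and shift that the SAP does not give. They do not show that the estimate is biased. They show that the model is unprotected against a departure that the SAP itself reports, and that protection costs nothing if the departure turns out not to matter.

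The point concerns additive background change only. It says nothing on whether phone delivery has a different effect, nor on selection from restricting the full analysis set to dyads who were assigned a coordinator.

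**What to change.** In model (1) and in the delta model, replace the municipality main effect by municipality-by-period fixed effects: 3 × 5 cells, with period defined by the calendar date of assessment. The treatment effect is then estimated only from sequences compared within the same municipality and period. Report the model with municipality and common period effects as a sensitivity analysis. State in the SAP the realised exposure schedule by municipality, group and period, and how the treatment indicator is coded from it.

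Cost: 15 cell parameters replace 3 (intercept and two municipality terms), which is 12 more than the model as written. A model with common period terms has 3 + 4 = 7, so against that it is 8 more. With complete data there are 315 × 5 = 1,575 observations. There is no loss of precision under the planned schedule, and the SE is about 2.5–5% larger under the assumed delays. For N = 240 and ρ = 0.1075, power for 7 h/week goes from 95.4% to 94.4% with group 2 delayed and from 98.6% to 98.2% with groups 2 and 3 delayed. These costs were not checked for the planned 20% loss to follow-up or for the non-normal model for hours. No new data are needed beyond assessment and start dates.

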The definition of treatment assignment as specified in section “Analysis sets” will be used in this section, too.

Deviations from the randomized treatment sequence occurred under the first Covid-19 lockdown, see section Modification History, Changes to the study protocol

Treatment duration

Each municipal coordinators are writing logs, and we will collect the data and calculate total hours of care by the coordinator, divided into different categories.

Descriptive statistics for the total hours of care by the coordinators will be presented.

Delivery of the intervention

One coordinator from the municipal per dyad

Efficacy

Primary efficacy analysis

The primary efficacy analysis variable caregiver burden is based on two variables. The first is RUD, divided in three categories: number of hours the last 30 days invested in personal, instrumental and supervisory care. The second is RSS measured as total score but also

specific and clustered items. Lower hours of informal care as well as lower score of RSS, indicates reduction in caregiver burden.

The null hypothesis states that there are no differences in burden and resource utilization between the LIVE intervention and usual care. The primary alternative hypothesis (H1) states that the LIVE intervention will improve caregiver burden and resource utilization compared with usual care. The secondary alternative hypothesis (H2) is that the LIVE intervention will provide more cost-efficient services than usual care.

H0: LIVE treatment = control

H1: LIVE treatment > control

H2: cost efficiency > control

where LIVE treatment denotes the proportion of caregivers experiencing improvement in care burden. The primary hypothesis will be statistically assessed by means of a χ^2 test on the one-sided significance level of 2.5% (corresponding to 5% two-sided).

We will plot the regression line to visualize the parallel effect for both treatment group and control group.

The significance level will be set to 2.5% (one-sided, corresponding to 5% two-sided), the corresponding level of one-sided CI is 97.5% (corresponding to 95% two-sided).

Missing data

We will pre-specify a list of baseline covariates that are likely associated with the missingness and the outcome, and adjust for these covariates in our primary analyses. This covariate-adjusted analysis will be valid under the missing at random (MAR) mechanism.

Sensitivity and robustness tests of regression analyses and economic evaluation

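### The primary mixed model treats dyads who share a municipal coordinator as independent; if caseloads exceed one and coordinators differ in effect, the standard error of the treatment effect is too small

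*SAP*

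**What the plan says.** **Allocation.** The section on randomization and blinding states: "Block randomization was performed using a computerized random number generator to allocate individual dyads to the three intervention sequences". Stratification is meant to ensure that "about one third of the dyads in each treatment sequence will be recruited from each municipality".

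**Delivery.** Under Causal model, the treatment indicator is defined as receiving help from a municipal coordinator. Under Delivery of the intervention the SAP says "One coordinator from the municipal per dyad". The number of dyads per coordinator is not given. The blinding text says that home care services and "coordinators will be informed about allocation sequence when their clusters entered the intervention period". Planned enrolment is "3 municipalities and 9 municipality districts".

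**Model.** Model (1) "adjusts for participant-level random effect" and contains no other random effect. Under Groups, municipalities, municipality is a fixed effect, and districts are left out: "This is not the case for district municipalities as we consider that the dyads are similar within municipalities". No coordinator term appears in the model, the covariate lists or the sensitivity analyses, and no reason is given for its absence.

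**The concern.** Dyads served by the same coordinator share that person's skill, time and way of working. This correlation arises after allocation and only while a dyad is treated, so randomising dyads individually does not remove it. It falls on the cells that identify β1. A participant intercept captures correlation within a dyad, not between dyads under one coordinator.

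If the correlation is present and unmodelled, the interval for β1 is too narrow. A trial with no average benefit would then be declared positive more often than the planned 5% two-sided.

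**Working it through.** **Inputs from the SAP:** 315 dyads, three sequences (105 each), five assessments, SD 20 h/week (variance 400), difference 7 h/week, two-sided 5%, 80% power, within-individual correlation 0.1075 (from the post-hoc sample size paragraph).

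**Assumed, because the SAP does not give them:** caseload m of 5 to 35 (35 = 315/9, that is, one coordinator per district or per municipality-by-sequence group of 35); coordinator ICC of 0.01 to 0.05 in treated periods; period effects in the model; treatment status kept on after the step.

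**1. The plan's own figure.** n per arm = 2 × 20² × (1.96 + 0.8416)² / 7² = 128.1, so 129 per arm and 258 in total. The t-based version gives 130 per arm, 260 in total, which is the SAP's number. It assumes independent dyads and has no clustering term.

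**2. Model standard error.** The treatment patterns are (0,1,1,1,1), (0,0,1,1,1) and (0,0,0,1,1). With compound symmetry at 0.1075 and variance 400, the model-based variance of β1 is 2.874, so its standard error is 1.695 h/week.

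**3. Add a coordinator effect with variance ICC × 400 in treated cells only.** The estimate is a weighted sum of observations. The weights on treated cells sum to one, split 0.591, 0.282 and 0.127 over the three sequences.
- Coordinators spread evenly over sequences: added variance = ICC × 400 × m/315. Dividing by 2.874, the true/model SE ratio = √(1 + 0.442 × m × ICC).
- Coordinators nested in one sequence: added variance = ICC × 400 × (m/105) × (0.591² + 0.282² + 0.127²) = ICC × m × 1.695. The ratio = √(1 + 0.590 × m × ICC).

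Type I error for an average effect of zero = 2 × [1 − Φ(1.96/ratio)].

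| m | ICC | Ratio, spanning | Type I | Ratio, nested | Type I |
|---|---|---|---|---|---|
| 5 | 0.01 | 1.011 | 5.3% | 1.015 | 5.3% |
| 5 | 0.05 | 1.054 | 6.3% | 1.071 | 6.7% |
| 6 | 0.01 | 1.013 | 5.3% | 1.018 | 5.4% |
| 6 | 0.05 | 1.064 | 6.6% | 1.085 | 7.1% |
| 12 | 0.01 | 1.026 | 5.6% | 1.035 | 5.8% |
| 12 | 0.02 | 1.052 | 6.2% | 1.068 | 6.7% |
| 12 | 0.05 | 1.125 | 8.1% | 1.164 | 9.2% |
| 35 | 0.01 | 1.075 | 6.8% | 1.098 | 7.4% |
| 35 | 0.05 | 1.332 | 14.1% | 1.426 | 16.9% |

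Splitting a group of 35 into caseloads of 12, 12 and 11 changes the nested values at m = 12 only slightly: 1.034, 1.067 and 1.160 for ICC 0.01, 0.02 and 0.05. At one dyad per coordinator the ratio is at most 1.015.

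**4. District intercept.** With dyads randomised individually and districts balanced over sequences, a random district intercept leaves the ratio at 1.000 and the error at 5.0% for any ICC. It is constant over time and cancels between sequences.

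**5. Cross-check on the 260.** In a two-arm design clustered only in the treated arm, n per arm = (20 × 2.8016/7)² × [2 + (m − 1) × ICC]. For m = 10 and ICC 0.02 this is 64.1 × 2.18 = 139.7, so 140 per arm and 280 in total. Over ICC 0.01 to 0.05 the total runs from 268 to 314.

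**The case against.** **The caseload is not in the document.** The SAP says one coordinator per dyad, and "when their clusters entered the intervention period" has both home care services and coordinators as its subject, so it may mean only the sequence groups. This stands: shared caseloads are implied, not stated. But one distinct coordinator for each of 315 dyads would fit that wording poorly.

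**The SAP's strict null.** If the intervention affects no one, coordinators cannot differ in effect and the error stays at 5%. This also stands. The inflation concerns an average effect of zero with coordinators that differ. When there is a true effect, the interval is still too narrow.

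**Tempting stronger readings that the SAP does not support:**
- *The SAP justifies omitting coordinators by the similarity of dyads.* That reason is given for districts only.
- *Omitting districts shrinks the standard error.* Under the stated individual randomisation, stratified by municipality, it does not (step 4). It would if whole districts were allocated to a sequence (ratio 1.125 to 1.526 for ICC 0.01 to 0.05). The nine districts and the timeline's groups of 35 might suggest this, but the randomization text says otherwise.
- *The type I error is about 18%.* That needs caseload 35, ICC 0.05 and a within-individual correlation of 0.5; the SAP's value is 0.1075.

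**The remedy has limits.** With only about nine coordinators, a variance component is poorly estimated. This is a reason for a small-sample correction, not for assuming independence.

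**Conclusion.** The point holds conditionally. Model (1) omits the one grouping that the intervention itself creates, and the SAP does not say why. If coordinators serve more than one dyad and differ in effect, the standard error of β1 is understated. The understatement is slight at small caseloads and low ICC, moderate at a caseload of 12, and large only at the extreme corner of the table.

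These sizes rest on assumed caseloads and ICCs, on the SAP's correlation and variance, on period effects in the model and on a normal reference distribution. The direction does not depend on the particular values chosen. This is an inexpensive improvement that protects the error rate, not a defect that invalidates the analysis.

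**What to change.** - State the number of dyads per coordinator and whether a coordinator serves dyads from more than one sequence.
- Link coordinator identity to each dyad's outcome record. The coordinators' logs should supply it, but the SAP does not say that this link exists.
- Add to model (1) a random coordinator effect that acts only in treated periods (coordinator identity multiplied by the treatment indicator). At minimum, name it as a sensitivity analysis of the primary result. Nesting in district is not needed.
- Use a small-sample degrees-of-freedom correction if coordinators are few, and report the estimated coordinator ICC.

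The cost is a few sentences of SAP text, one identifier and one variance component. Intervals will be somewhat wider, and with few coordinators the variance component will be imprecise, so the SAP should also say what is done if the model does not converge.
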